Days -60 to -2	Days -49 to -1	Day -1	Days 1 to 21	Day 22		Day 41	Days 42 to 62	Day 63	Day 73 (±2)
←—Intermittent Confinement—→ Confinement on Days -1 to 2, 11, 20 to 22, 41 to 43, 52, and 61 to 63									

(a) Subjects with MCI or mild AD on stable donepezil (10 mg) treatment or who consent to a donepezil run-in period of 5 mg dose for 28 days and titrate up to 10 mg for at least 21 days. Subjects with previous MCI/AD diagnosis who have been treated with 5 mg for at least 28 days prior to Screening may consent to a donepezil run-in period of 10 mg for at least 21 days.

Figure 6.g Schematic Study Design for Cohort 17

Pretreatment Period		Treatment Periods 1, 2, and 3 (a)		Final Visit	Follow-Up
Screening	Check-in	Single Dose/PK	PK		Follow-up Telephone Call
Days -28 to -2	Day -1	Day 1	Days 2 to 5 and 8	Day 8 Period 3	Day 12 (±2) Period 3
		Washout (b) Days 2 to 21 of Periods 1 and 2 only			
	← Intermittent Confinement →				
	Confinement on Days -1 to 4 and outpatient PK visit on Day 8				

(a) Visit Day count shown as relative to Day 1 of each treatment period.

(b) The total washout period will be 21 days from the time of dosing.

For Cohorts 7 to 8 and 10 to 12, the dosing duration and for Cohorts 9 and 13 to 16, the dosing and/or washout duration may be adjusted if PK data from the SRD part indicate that a different period may be more appropriate (ie, 5 times the observed $t_{1/2z}$). For Cohort 17, washout period may be adjusted if PK data from previous cohorts warrants so.

The planned duration of dosing in all MRD cohorts will be of 21 days. If warranted based on emerging PK data (ie, based on the observed range of $t_{1/2z}$ values) and assuming acceptable safety and tolerability in preceding cohorts, the duration of TAK-071 dosing may be reduced to at a minimum of 14 days or extended for up to a maximum of 28 days.

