For relative BA of tablet formulation (compared to DIC) and the FE cohort (Cohort 17), TAK-071 will be administered as DIC and tablet formulations in a cross-over design as 3 regimens (Regimens A, B, and C). For all 3 regimens study drug will be administered after an overnight fast of at least 8 hours on each dosing day. Subjects randomized to Regimens A and B will remain fasted prior to dosing; however, subjects assigned to Regimen C should start the standard high fat meal (~ 50% fats) 30 minutes prior to administration of the drug product and finish the meal within 25 minutes. On dosing days, the source documentation and the eCRF will record whether the subjects consumed 100% of their breakfast (or the approximate percentage of the meal consumed: 0%, 25%, 50%, or 75%) during the fed regimen (Regimen C). Subjects in all 3 regimens will fast for an additional 4 hours after dosing. Water will be allowed ad libitum after 2 hours postdose.

Subjects in Regimen C, randomized to receive drug administration with food, will consume a high-fat (approximately 50% of the total caloric content of the meal), high-calorie (approximately 1000 calories) breakfast beginning 30 minutes prior to study drug administration, consume the

meal within 25 minutes and receive study drug 30 minutes after the start of the meal. Subjects will then fast from food until approximately 4 hours postdose at which time a standard lunch will be served. Water will be allowed ad libitum after 2 hours postdose. The content of a sample high-fat breakfast is listed in [Table 7.b](#).

Table 7.b **Content of a Standard, High-Fat Breakfast**

2 fried or scrambled eggs
2 strips bacon
2 slices of toast with 2 pats of butter
4 oz (113 g) hash browns (fried potato)
240 mL whole milk

7.4.2 Cohort 16

Based on the preliminary results from cohort 17, food did not appear to affect the systemic exposure to TAK-071. Therefore, TAK-071 and donepezil can be given with or without food. However, on the days of blood draws for clinical laboratory tests, TAK-071 and placebo will be administered with approximately 240 mL of water after a fast of at least 8 hours.

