8.1.3 Dose and Regimen

The investigator or investigator's designee will instruct the subject on dosing procedures. All dosing will occur while subjects are in the clinic under the supervision of the principal investigator

or designee (except Days -18 to -11 during Cohorts 10 to 12 where the subject will self-administer donepezil and Days 3 to 10, 12 to 19, 43 to 50, and 52 to 59 during Cohort 16 where the subject will self-administer TAK-071 or placebo each morning at home). The doses taken in the clinic will be administered to the subjects by the investigator or investigator's designee. The exact time of dose will be recorded in the source documents and on the appropriate eCRF.

The planned initial dose of TAK-071 or matching placebo for Cohort 1 is 1 mg. TAK-071 is dosed on the morning of Day 1 after fasting for at least 8 hours. Cohorts 2 through 6, 18, and 19 will escalate through the SRD levels and Cohorts 7 through 9 through the MRD dose levels. Additionally, Cohorts 10 to 12 will be pretreated for 3 weeks with 5 mg donepezil orally continuing through Day 21. In healthy subjects in Cohorts 10 to 12, donepezil will be administered in the morning, shortly before or after TAK-071; the precise relative timing will be confirmed once TAK-071 PK data are available. Cohorts 9 and 13 through 15 will have 1 dose of TAK-071 on Day 1 followed by a 7-day washout period before administration of 21 daily doses of TAK-071. Subjects in Cohorts 20 to 22 will be administered as a single dose of TAK-071 or placebo on Day 1, and a single dose of donepezil or placebo approximately 24 hours later on Day 2.

In Cohort 16, subjects with MCI or mild AD who are stable on donepezil will be randomized to 1 of 2 possible treatment sequences consisting of 2 periods and 2 treatments, alternating in a crossover fashion. In each period, subjects will receive 1 of the following treatments: TAK-071 QD for 21 days (Treatment A) or 21 days of matching placebo (Treatment B). Background 10 mg QD donepezil treatment will be administered in the evening just before bedtime.

In Cohort 17 (Relative BA and FE), TAK-071 DIC or tablet will be administered as a single dose (Regimen A, B, and C) in a cross-over design over 3 periods, with a 21-day washout after each treatment. The planned dose is 10 mg in each of the 3 periods. Diet assigned to each regimen is described in Section 7.4.

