9.3.3 Treatment Phase/Washout Phase

For Cohorts 1 to 6 and 18 to 22, the Treatment Phase will consist of a single dose of study drug (for Cohorts 20 to 22 donepezil will be administered approximately 24 hours after the TAK-071 dose). For Cohorts 7, 8, and 10 to 12, the Treatment Phase will consist of 21 QD doses of study drug. For

Cohorts 9 and 13 to 15, the Treatment Phase will consist of a single dose of study drug, followed by a washout period of 7 days and 21 QD doses of study drug.

For Cohorts 9 and 13 to 15, the washout and/or dosing duration may be adjusted with additional day(s) if PK data from the SRD part indicate that a longer duration may be more appropriate.

For Cohort 16 the treatment duration will consist of 21 QD doses of Treatment A (TAK-071) or B (placebo) in Period 1, a 21-day washout, and then 21 daily doses of Treatment A or B in Period 2. Treatment assignments will be switched between Period 1 and 2. A donepezil run-in period of 49 days, prior to starting Treatment A, may be included if the subject is diagnosed at Screening.

For Cohort 17, the treatment duration will consist of a single dose of study drug in each of 3 periods. Washout period of 21 days will follow Periods 1 and 2.

The washout and/or dosing duration may be adjusted with additional day(s) if PK data from the SRD part indicate that a longer washout may be more appropriate.

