(i) A standard 12-lead ECG will be recorded at Screening, Check-in (Day -1), Days 1 and 8 (TAK-071 predose [within 60 minutes prior to dosing] and at 0.5, 1, 2, 4, and 8 hours postdose). On the remaining days during confinement 12-lead ECG be recorded (upon morning rising), or ET. Single ECGs will be taken at all visits.

(j) DIC will be dispensed for treatment.

(k) Blood samples for PGx analysis will be collected as follows: 6 mL for DNA on Day 1; 2x2.5 mL for RNA predose TAK-071 on Day 1, predose TAK-071 on Day 8, and 12 hours postdose on Day 28.

(l) Blood samples (3 mL/sample into EDTA coated tubes) for plasma measurement of TAK-071 will be collected predose (within 30 minutes prior to dosing) and specified time points outlined in Section 9.1.15.1.

(m) Urine samples for PK analyses will be collected predose within approximately 1 hour of dosing and specified time points outlined in Section 9.1.15.2.

(n) PTEs will be collected from signing of informed consent up until dosing on Day 1.

(o) Any event after dosing on Day 1 will be captured as an AE.

(p) Bowel function will be assessed using the BSF scale and daily stool count.

(q) C-SSRS will be determined as indicated. If clinically significant at Final Visit, C-SSRS will also be determined as part of the Follow-up Visit.

ET=Early Termination Visit, HBsAg=hepatitis B surface antigen, HCV=hepatitis C virus.

- (a) Only subjects in donepezil run-in period will have these assessments.
- (b) A PK blood sample should be collected at the Early Termination Visit if possible.
- (c) Follow-up will occur by telephone on Day 73 (± 2) unless abnormal clinically significant findings are observed upon discharge. In these cases, subjects must then be brought back to the clinic for re-evaluation per investigator's discretion.
- (d) Vital signs (oral temperature, respiration, pulse, and blood pressure) will be obtained as indicated. In addition, orthostatic blood pressure will be measured at predose and at 2, 4, 6, 8, and 12 hours postdose in the first 24 hours after the initial dose of TAK-071 and then afterwards on Days 2, 11, 20 to 22, 41 to 43, 52, and 61 to 63 (upon morning rising or arrival for outpatient visit) or ET as detailed in Section 9.1.6.
- (e) Height and BMI will be collected at Screening only.
- (f) All ongoing medications will be recorded from Screening and throughout the study.

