- (g) Blood and urine samples for clinical laboratory tests (hematology, coagulation, serum chemistry, urinalysis) will be collected as indicated. On Days 1 and 42, the urine sample for urinalysis will be taken at predose (within 2 hours prior to dosing) and the blood sample for these tests will be taken 1 hour postdose. On all other days, when the subjects are confined at the phase 1 unit, blood and urine samples will be taken predose upon rising in the morning under fasted condition.
- (h) FSH concentration will be obtained from postmenopausal women (defined as continuous amenorrhea of at least 2 years and not surgically sterile). The result must be >40 IU/L for the subject to be enrolled.
- (i) A standard 12-lead ECG will be recorded at Screening, Check-in (Day -1), Days 1, 21, 42, and 62 (TAK-071 predose [within 60 minutes prior to dosing] and at 0.5, 1, 2, 4, and 8 hours postdose), Days 2, 11, 20 to 22, 41 to 43, 52, and 61 to 63 (upon morning rising or arrival for outpatient visit) or ET. Single ECGs will be taken at all visits.
- (j) DIC will be dispensed for treatment.
- (k) Subjects must be receiving ongoing donepezil therapy (10 mg) in the evening for a minimum of 21 days prior to Check-in and during the study (if subjects were receiving 5 mg dose at Screening, it should be up-titrated to 10 mg on Day -21). Alternatively, subjects may be diagnosed at Screening and start donepezil run-in for 49 days prior to Day -1, and on stable 10 mg dose of donepezil 21 days prior to Day -1. Subjects will continue with their donepezil therapy during the TAK-071 Treatment Period.
- (l) Blood samples for PGx analysis will be collected as follows: 6 mL for DNA on Day 1; 2×2.5 mL for RNA predose TAK-071 on Days 1 and 42 and 12 hours postdose on Days 21 and 62.
- (m) Blood samples (3 mL/sample into EDTA coated tubes) for plasma measurement of TAK-071 will be collected predose (within 30 minutes prior to dosing) and specified time points outlined in Section 9.1.15.1.
- (n) Blood samples (4 mL/sample collected into sodium heparin tubes) for the measurement of donepezil will be collected predose (within 30 minutes prior to TAK-071 dosing) and specified time points outlined in Section 9.1.15.1.
- (o) Urine samples for PK analyses will be collected predose within approximately 1 hour of dosing and specified time points outlined in Section 9.1.15.2.

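### Protocol 8.1.3 lists the Cohort 16 Period 2 home-dosing days one day early, so Days 43 and 52 are both home and clinic days and Days 51 and 60 are neither

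*Protocol*

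**What the plan says.** Protocol 8.1.3 sets clinic dosing as the rule: "All dosing will occur while subjects are in the clinic under the supervision of the principal investigator" or a designee. It then lists the exceptions, which for Cohort 16 are "Days 3 to 10, 12 to 19, 43 to 50, and 52 to 59 during Cohort 16 where the subject will self-administer TAK-071". Placebo follows the same list, and these home doses are morning doses. This is the only place where the home days are listed.

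Figure 6.f (Protocol 6.1) puts Period 2 dosing on Days 42 to 62 and gives the clinic days: "Confinement on Days -1 to 2, 11, 20 to 22, 41 to 43, 52, and 61 to 63". Section 9.3.3 requires a 21-day washout "and then 21 daily doses of Treatment A or B in Period 2". Table 9.u uses the same visit days and shows a clinical laboratory sample on Days 43 and 52. The Cohort 16 footnotes in Appendix A agree: orthostatic readings continue "afterwards on Days 2, 11, 20 to 22, 41 to 43, 52, and 61 to 63", and serial ECGs are on "Days 1, 21, 42, and 62 (TAK-071 predose" and postdose).

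Laboratory days carry two further rules. Section 7.4.2 says that "on the days of blood draws for clinical laboratory tests, TAK-071 and placebo will be administered with approximately 240 mL of water", and it requires an 8-hour minimum fast beforehand. Appendix A footnote (g) says that, apart from Days 1 and 42, on days of confinement "blood and urine samples will be taken predose upon rising in the morning under fasted condition".

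**The concern.** Section 8.1.3 is an operative dosing instruction for patients with MCI or mild AD who take most of their doses unsupervised. Its Period 2 days contradict the visit schedule in two ways.

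- **Days 43 and 52** are named as home days but are clinic days with laboratory samples. On Day 43 the patient is in the unit. On Day 52 a morning dose at home before the visit would turn a predose sample into a postdose one and leave the required fast unsupervised. The matching Period 1 visit, Day 11, is correctly left off the home list.
- **Days 51 and 60** are not home days, so the default sends the dose to the clinic, where no visit is scheduled. Day 60 is two days before the Day 62 steady-state profile, and steady-state Cmax and AUC24 are primary PK parameters.

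The same shift appears elsewhere. The urine notes in Protocol 9.1.15.2 and SAP 7.10.3 put the predose void on Day 61, while the collection in the same tables is on Day 62. In the SAP, the sample-timing sentence in 7.12.2 uses Day 41, the orthostatic list in 7.12.3 uses 40 to 42, 51 and 60 to 62, and 7.12.4 puts serial ECGs on Days 41 and 61.

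**Working it through.** **1. Which days should be home days.** Home days = dosing days minus clinic days.

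| | Dosing days | Clinic dosing days | Home days required | Home days in 8.1.3 |
|---|---|---|---|---|
| Period 1 | 1–21 | 1, 2, 11, 20, 21 | 3–10, 12–19 (16) | 3–10, 12–19 (16) |
| Period 2 | 42–62 | 42, 43, 52, 61, 62 | 44–51, 53–60 (16) | 43–50, 52–59 (16) |

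Period 1 reproduces the plan exactly: 16 + 5 = 21 doses, with no overlap. In Period 2 the listed home days plus the clinic days give 16 + 5 − 2 = 19 distinct days. The overlap is {43, 52} and the uncovered days are {51, 60}. Adding 1 to each listed day gives the required set. So does adding 41 to each Period 1 home day, since Period 2 starts 42 − 1 = 41 days after Period 1.

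**2. Where the list comes from.** Suppose Period 2 ran on Days 41 to 61 with clinic days 40 to 42, 51 and 60 to 62, the days still printed in SAP 7.12.3 and 7.12.4. The home days would be 43–50 and 52–59, exactly the list in 8.1.3. Leftover numbering is therefore the likely source. This is an inference, because the documents do not set out that schedule.

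**3. Which start day is right.** The washout is at least 21 days (6.1.3). The last Period 1 dose is on Day 21; 42 − 21 = 21, but 41 − 21 = 20. The PK, urine-collection and laboratory tables and the Appendix A footnotes also use Day 42.

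**4. Size if the two uncovered doses were missed (hypothetical).** Assume linear one-compartment kinetics. The half-lives of 65 and 140 h are the thresholds in 6.2.2.2 for shortening or extending dosing; neither is an observed value. With k = ln 2 / half-life and r = exp(−24k), the share of Day 62 AUC24 contributed by the dose on day d is r^(62 − d) / S, where S = (1 − r^21) / (1 − r).

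| Half-life | r | S | Day 60: r²/S | Day 51: r¹¹/S | Both |
|---|---|---|---|---|---|
| 65 h | 0.774 | 4.41 | 0.136 | 0.014 | 0.150 |
| 140 h | 0.888 | 8.19 | 0.096 | 0.033 | 0.129 |

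The loss is 13% to 15%, most of it from Day 60. Only sequence BA takes TAK-071 in Period 2, which is about 3 to 4 subjects if 6 to 8 are split evenly. The Day 21 profile in sequence AB would be unaffected.

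**5. SAP against itself and Appendix A.** SAP 7.12.2 and 7.12.3 each list the Period 2 visits correctly as Days 41, 42, 43, 52, 61, 62 and 63. The Day 41 urinalysis and blood timing in 7.12.2, and the orthostatic days in 7.12.3, contradict those lists within the same paragraphs. The ECG days in 7.12.4 contradict Appendix A footnote (i).

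**The case against.** The list in 8.1.3 governs where a dose is taken, not whether it is taken. The section itself calls for once-daily dosing for 21 days, as do 6.1.3 and 9.3.3, and a day off the home list defaults to the clinic. The number of home days, 16, is right. A site dosing daily would probably notice the gap, and dose dates and times are recorded and listed, so an omission would be visible. Footnote (g) ties predose sampling to confinement, and footnotes (d) and (i) allow for arrival at an outpatient visit, so staff following Appendix A would have reason not to let a patient dose before the Day 52 samples. On the analysis side, the SAP is to be read with the protocol, and SAP 7.1.3 counts Cohort 16 study days from the dosing date in each period.

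Most of this stands, and it rules out two stronger readings. A reader might infer that 8.1.3 provides for only 19 doses and so builds in an exposure loss. It does not: no text directs a missed dose. A reader might also infer that the SAP would drop the orthostatic readings on Days 43, 52 and 63 as unscheduled. That is not supported, because 7.12.3 names those days as vital-sign visits and its summary rule admits scheduled visits. Nor is any loss of ECG data shown.

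The contradiction itself remains. Figure 6.f lists Day 52 as a confinement day, so the predose rule applies to it. Two required doses have no workable place of administration under the written instructions.

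**Conclusion.** Section 8.1.3 is wrong as written for Period 2: two days are double-assigned and two required doses have neither a home listing nor a visit. This rests on Figure 6.f, Table 9.u and the Appendix A footnotes; the Cohort 16 visit grid in Appendix A could not be checked. The Day 52 conflict with fasted, predose sampling follows directly from the text. The 13% to 15% fall in Day 62 AUC24 is conditional on two missed doses, on linear one-compartment kinetics and on a half-life of 65 to 140 h. It shows what is at stake in sequence BA and is not a forecast. The urine-void notes and the SAP day lists are inconsistent with Appendix A, and partly with the SAP's own visit lists, but no loss of data from the summaries is shown. The point is a low-severity correction that is worth making because it concerns a dosing instruction.

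**What to change.** 1. Protocol 8.1.3: change the Period 2 home days to 44 to 51 and 53 to 60.
2. Protocol 9.1.15.2 and SAP 7.10.3, urine notes for Cohort 16: change Day 61 to Day 62.
3. SAP 7.12.2 to 7.12.4: use the Appendix A days. Urinalysis and blood timing go on Days 1 and 42, serial ECGs on Days 1, 21, 42 and 62, and Period 2 orthostatic and other ECG days on 41 to 43, 52 and 61 to 63.

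The cost is day numbers in one protocol sentence, two notes and three SAP sections, with no new visit, sample, form or subject. Any home-dosing instructions already prepared from 8.1.3 should be checked. The plan has Cohort 16 still enrolling during the interim analysis, kept blinded and analysed later (Protocol 13.2.1, SAP 7.14), so the correction can precede its analysis.

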8.1.4 Overdose

An overdose is defined as a known deliberate or accidental administration of investigational drug, to or by a study subject, at a dose above that which is assigned to that individual subject according to the study protocol.

All cases of overdose (with or without associated AEs) will be documented on an Overdose page of the eCRF in order to capture this important safety information consistently in the database.

Cases of overdose without manifested signs or symptoms are not considered AEs. AEs associated with an overdose will be documented on AE CRF(s) according to Section 10.0, PTEs and AEs.

SAEs associated with overdose should be reported according to the procedure outlined in Section 10.2.2, Collection and Reporting of SAEs.

In the event of drug overdose, the subject should be treated symptomatically.

8.2 Investigational Drug Assignment and Dispensing Procedures

Subjects will be assigned, in the order in which they are randomized into the study, to receive their treatment according to the randomization schedule allocated to the site. The Randomization Sequence Number will be entered onto the eCRF.

For each dosing cohort in SRD, MRD, and BA/FE parts, randomized subjects will be assigned a 5-digit randomization number in the order which they are enrolled. Randomization sequence numbers will be XYY01 to XYY08 (Cohorts 7 to 12) or XYY06 (Cohorts 13 to 15), where X refers to SRD (Part 1) or MRD (Part 2) and Y refers to cohort number.

For example:

- Subjects in SRD Cohort 1 will have randomization sequence numbers 10101 to 10108, and subjects in SRD Cohort 2 will have numbers 10201 to 10208.
- Subjects in MRD Cohort 7 will have randomization sequence numbers 20701 to 20708, and subjects in MRD Cohort 11 will have numbers 21101 to 21108.
- Subjects in MRD Cohort 13 will have randomization sequence numbers 21301 to 21306.
- Subjects in BA/FE Cohort 17 will have randomization sequence numbers 21701 to 21712.
- Subjects in Cohort 20 will have randomization sequence numbers 12001 to 12012.

If a subject needs to be replaced, the replacement subject will receive the same treatment or treatment sequence of the subject being replaced. The replacement randomization number will be 50 larger than the randomization number of the subject who is being replaced. For example, randomization number 10251 will be used for the subject who replaces the subject who had randomization number 10201, using the same treatment or treatment sequence in Cohort 2.

This 5-digit number will be used by the clinical site to facilitate the prelabeling of PK samples and will be the only subject identifier used on all PK and/or PD sample collections. It should also be contained on the PK transport vials shipped to the bioanalytical laboratory and will be used by the laboratory to report the subject data results. This 5-digit number should only be used for the purposes described in this section. It does not replace the 3-digit subject number that is assigned at the time the informed consent is obtained and used for all other procedures to identify the subjects throughout the study.

Study drugs will be dispensed in the clinic under the supervision of the investigator or designee.

